7.1 Plan of Investigation

A. Centre Pathway Review

We have 15 MND centres committed to participating in PROGAS. A provisional survey of the centres has identified that 360 gastrostomies are performed for MND patients in the UK per year. The first component of PROGAS will be to perform a detailed survey of current practice regarding gastrostomy pathways at each centre. A questionnaire will be completed by the director of each centre capturing data regarding indication for gastrostomy, timing, and type of gastrostomy. This survey will highlight current practice, good practice points and will enable refinement of the data analysis plan of the main phase of the study. The centre director will also identify a “local champion” who will assist in recruiting patients and liaise with the central study co-ordinator who will be based in Sheffield.

B. Prospective evaluation of Gastrostomy

Following ethical and research governance approvals, participants will be recruited into PROGAS from all participating sites over a period of 21 months. All centres will be encouraged to maintain their usual practice and protocols for gastrostomy provision.

i) Patient enrolment

The study will be discussed with patients and carers, when a gastrostomy is being considered by the clinical team as part of their normal standard care. Patients and carers will be asked to consent to the study at the time of referral for gastrostomy. We will aim to recruit 504 patients and carers over 21 months. This figure is based on 80% (i.e., the anticipated patient response rate) of the 630 eligible patients seen according to the provisional survey of centres undertaken.

ii) Pre Gastrostomy Patient Evaluation

Once patients are successfully recruited and consented into PROGAS, the local investigator will complete a Pre Gastrostomy Patient evaluation form. This form is designed to capture routine data already being recorded in clinics, including demographic and functional characteristics, nutritional and respiratory status and gastrostomy-related data.

iii) Peri-Procedure Evaluation

Patients will then undergo the gastrostomy procedure. At the end of the procedure, either the local investigator or a member of the team performing the gastrostomy insertion will complete a Peri-procedure evaluation form. This form will capture the details of the procedure as well as any complications that occur during the procedure.

iv) Follow Up Patient Evaluation

Patients will attend their usual follow up appointments at their centre. Each patient will be followed up over 12 months following gastrostomy. At the visits which coincide nearest with 3 months and 1 year post gastrostomy, follow up evaluation forms will be completed. Data on weight, gastrostomy related complications, ALS-FRS and survival will be collected. At the follow-up visits patients and carers will complete quality of life assessment and carer burden assessments respectively.

v) *Quality of life for patients and carers*

Aspects related to the quality of life of patients, and their carers, following gastrostomy will be assessed with a combination of qualitative and quantitative tools. The qualitative sub-study at Sheffield and Leeds sites will evaluate the gastrostomy experience from the perspective of the patients and their carers. In addition, at baseline and at the following up visits patients and carers at all participating sites will complete quality of life and carer burden assessments respectively, as outlined in the following section.

All forms will be anonymised by the local champion at each site and will be returned to the Sheffield-based PROGAS co-ordinator.

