PROGAS has been designed in response to particular uncertainties faced by ourselves as healthcare practitioners, and as a result of the research priorities identified by the Dementias and Neurodegenerative Diseases Research Network (DeNDRoN) Clinical Studies Group for MND and the Motor Neurone Disease Association (MNDA). For PROGAS we have adopted an all-inclusive approach, inviting as many MND care centres in the UK, as possible. Following ethical and research governance approvals, PROGAS will run for 3 years. Participant recruitment will occur for the first 21 months. The follow up period will take 12 months. Finally, a 3-month period at the end of the project will enable analysis of data, dissemination of findings and report writing. A more detailed project timetable is available in section 19 of this protocol.

A mixed methodology approach will be employed:

(a) Quantitative questionnaires will be used to evaluate the UK clinical practice in relation to gastrostomy in patients with MND.

(b) Qualitative interviews will be used to illuminate unexplored issues surrounding the experience of patients, and their informal carers, with regard to gastrostomy and its impact on quality of life.

We have chosen this methodology approach as it enables us to use quantitative questionnaires designed to investigate issues apparent from our pilot work and clinical experience, as well as allowing the opportunity for new, previously unrecognised issues important to the patient and the carer to be identified and explored through qualitative interviews. The quantitative part of the study will form the main study and will be conducted with participants (i.e., patients and their carers) from all participating sites. The qualitative part of the study will form a smaller component and will be conducted only at the MND Care and Research Centres in Sheffield and Leeds, with patients and their informal carers.

6 Background and Rationale

Background

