This form will be completed at the end of the gastrostomy procedure, either by the local champion or the member of the team performing the gastrostomy insertion. The form is designed to capture the details of the procedure with regard to staffing; gastrostomy equipment; drugs given; patient monitoring and respiratory support; as well as, any complications that occur during the procedure.

iv) 3-month Follow Up Patient Evaluation Form (see Appendix 4)

This form is designed to capture data with regard to gastrostomy complications occurred prior to patient's hospital discharge and those occurred after the hospital discharge up to the 3-month patient evaluation. Weight and ALSFRS-R for each patient will also be recorded. This form will be completed by the local champion after a patient's usual follow up visit which coincides nearest with 3 months post gastrostomy.

v) 12-month Follow Up Patient Evaluation Form (see Appendix 5)

This form is designed to capture data with regard to gastrostomy complications occurred in the period of time between the 3-month patient evaluation and the 12-month patient evaluation. Weight and ALSFRS-R for each patient will also be recorded. This form will be completed by the local champion after a patient's usual follow up visit which coincides nearest with 12 months post gastrostomy.

vi) McGill Quality of Life Questionnaire (MQOL) (see Appendix 7)

This is a well-established questionnaire, designed in the context of palliative care, to identify the health-related quality of life of patients with a terminal illness. It balances physical and non-physical aspects of quality of life, and includes both positive and negative influences on quality of life [53]. This questionnaire will be completed by patients at baseline and at 3 months post gastrostomy.

vii) Modified Caregiver Strain Index (MCSI) (see Appendix 8)

This is a well-established questionnaire, designed to identify the strain levels among informal carers of patients with long-term illness. It will be used in this study to assess the quality of life of the main carer of the patient and the impact that the treatment is having on the carer [54]. It will be completed by carers at baseline and at 3 months post gastrostomy.

viii) Gastrostomy-specific questionnaire (Gastro-Qu) (see Appendix 9)

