Once consented and successfully recruited into the study the participants will be further informed verbally about the next stages of PROGAS by the local researcher and undergo the gastrostomy procedure as scheduled. Data will be collected, by a member of the research team, before and following the gastrostomy procedure with the completion of the pre-procedure and the peri-procedure gastrostomy patient evaluation forms, respectively. Following hospital discharge, the participants will continue their standard visits (approximately every 2-3 months) to the neuromuscular clinic as part of routine clinical care.

For this study data will also be collected, by a member of the research team, 3 months and 1 year following gastrostomy.

During their participation into PROGAS, patients will be asked to complete a health-related quality of life questionnaire (MQOL) twice (at baseline and approximately at 3 months following gastrostomy), and a gastrostomy-specific questionnaire once (approximately at 3 months following gastrostomy). Participating carers will be asked to complete a quality of life questionnaire (MCSI) twice (at baseline and approximately 3 months following gastrostomy). Both patients and carers will be given freepost/pre-paid envelopes to return the questionnaires to the study's central co-ordinator.

The recruitment process of patients and carers for the qualitative component of PROGAS at Sheffield and Leeds MND Care and Research Centres will be similar to the process described above. Once consented and recruited, participants will be contacted by the local researcher by telephone (approximately 3 months following the gastrostomy procedure) to arrange with each one a date and time for a face-to-face interview at a place of each participant's choice. For this part of PROGAS, we will aim to recruit 10 patients and 10 carers. Quantitative data will be collected as described for the other sites. A detailed visual representation of the recruitment process is shown in the following chart (Chart 1).

[figure not shown]

Chart 1: Participant recruitment flow chart

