7.5 Study Outcomes

Primary:

- i) *Difference in the mortality rate in the first month following gastrostomy in PEG and PIG/RIG patients.*

Secondary:

- i) *Difference in the complication rate (classified in groups according to seriousness and time of occurrence) following gastrostomy in PEG and PIG/RIG patients.*
- ii) *Median survival time from (a) placement of feeding tube, (b) symptom onset, and (c) time of diagnosis of the disease in PEG and PIG/RIG patients.*
- iii) *Nutritional status changes (weight and BMI) following gastrostomy in PEG and PIG/RIG patients.*
- iv) *Self-perceived quality of life changes (measured by MQOL, gastrostomy questionnaire and qualitative interviews) following gastrostomy in PEG and PIG/RIG patients.*
- v) *Change in carer quality of life as measured by MCSI and qualitative interviews.*

Analysis will also include looking into how factors, such as (a) respiratory status, (b) site of symptoms onset, and (c) stage of disease, influence safety and survival following gastrostomy in PEG and PIG/RIG patients.

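### Survival is recorded only to about 12 months after the tube although the study collects data to month 33, which serves the median-survival outcome poorly

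*Protocol*

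**What the plan says.** Protocol Section 7.1 B(iv) sets the observation window: "Each patient will be followed up over 12 months following gastrostomy". Survival is among the items collected at the two follow-up evaluations. Section 7.4 names the same two time points, "3 months and 1 year following gastrostomy". Section 7.2 ties the last form to the "usual follow up visit which coincides nearest with 12 months post gastrostomy". That form has a field for date of death. No later contact or status check is described.

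Section 5 gives the calendar: "Participant recruitment will occur for the first 21 months", "The follow up period will take 12 months", and "a 3-month period at the end of the project will enable analysis of data".

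Secondary outcome (ii) in Section 7.5 is "Median survival time from (a) placement of feeding tube, (b) symptom onset, and (c) time of diagnosis of the disease", compared between PEG and PIG/RIG. Section 7.7 reads these medians from Kaplan-Meier curves and adds Cox regression for predictors of survival. The protocol states no expected median after the tube and no expected number of deaths. Its sample size rests on 30-day mortality alone.

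**The concern.** A Kaplan-Meier median from tube placement exists only if the estimated survival of the group falls to 50% within the period observed. With about 12 months per patient, a group whose true median lies near or beyond 12 months may have no reportable median. The longer-surviving group is the likelier to be affected, and that is the group the comparison most needs to describe.

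The first recruits reach their 12-month form up to 21 months before the last recruit does. They remain under the same centres, with routine visits about every 2-3 months (Section 7.4). Deaths in that interval would add precision to the comparison of methods and to the Cox analysis, but nothing in the protocol collects them. An analysis plan cannot recover death dates that were never recorded.

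**Working it through.** **Plan's own figures.** Section 7.1: 360 procedures a year × 21/12 = 630; 630 × 0.80 = 504, as stated. Section 5: 21 + 12 = month 33, and + 3 = month 36, the stated 3 years. With a common close at month 33, follow-up would run from 12 to 33 months, mean 22.5.

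**Assumptions, because the documents give no post-tube median.** True medians *m* of 6 to 18 months; exponential survival with rate λ = ln 2 / *m*; even accrual over 21 months; tube placed at entry; 504 patients, 252 per group; no other losses.

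**Is the median reached by month 12?** Survival at 12 months is S = 2^(−12/*m*). The median is reached if at most 126 of 252 patients survive 12 months (exact binomial).

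| True median (months) | S at 12 months | Chance median is reached |
|---|---|---|
| 9 | 0.397 | >99% |
| 10 | 0.435 | 98% |
| 11 | 0.469 | 85% |
| 12 | 0.500 | 53% |
| 13 | 0.527 | 21% |
| 15 | 0.574 | 1% |
| 18 | 0.630 | about 0% |

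With 150 in a group the pattern is the same: above 99% at 9 months, 53% at 12, 4% at 15.

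**Deaths observed.** To 12 months: 504 × (1 − 2^(−12/*m*)). To a common close at month 33: 504 × [1 − (e^(−12λ) − e^(−33λ)) / (21λ)].

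Example, *m* = 12: λ = 0.0578, e^(−12λ) = 0.500, e^(−33λ) = 0.149, 21λ = 1.213. Deaths to month 33 = 504 × (1 − 0.351/1.213) = 358. Deaths to 12 months = 504 × 0.5 = 252.

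| True median | To 12 months | To month 33 | Share of obtainable deaths not collected |
|---|---|---|---|
| 6 | 378 | 457 | 79/457 = 17% |
| 9 | 304 | 405 | 101/405 = 25% |
| 12 | 252 | 358 | 106/358 = 30% |
| 15 | 215 | 319 | 104/319 = 33% |
| 18 | 186 | 286 | 100/286 = 35% |

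Under a constant hazard the share cannot exceed 1 − 12/22.5 = 46.7%. With Weibull shapes from 0.8 to 1.5 and the same medians it runs from 12% to 48%. Tubes are placed some time after consent, so the true gain would be slightly smaller.

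**Precision at a median of 12 months.** SE of the log hazard ratio = √(4/deaths): √(4/252) = 0.126 against √(4/358) = 0.106. For an illustrative hazard ratio of 0.75, two-sided 5%, power is 63% against 78%.

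**What the protocol's own mortality figures allow.** If the 30-day rates in Section 7.6 persisted as a constant monthly hazard (an assumption), 4% gives a median of ln 0.5 / ln 0.96 = 17 months and 12-month survival of 0.96^12 = 61%, so the median is not reached. A rate of 9% gives about 7.3 months and 32%, so it is reached. The top PEG figure, 25%, gives about 2.4 months.

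**The case against.** Fixed 12-month follow-up is a legitimate design, stated consistently throughout the protocol. The primary outcome and the sample size concern one-month mortality and are untouched. A median reported as not reached is a valid result, and an analysis plan could report 12-month survival or a restricted mean instead. All of this stands. It makes the point an improvement to a secondary outcome; the protocol does not contradict itself here. A different summary would still leave the later deaths uncollected.

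A reader might infer more in four ways, none of which the documents support.

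- *That the study cannot report median survival.* No post-tube median is given, and the cited mortality rates fit medians on either side of 12 months. If the median is 9 months or less it is safely reached and only precision is lost. The calculation covers the tube-placement clock only. On the clocks from onset and diagnosis, 12 months after the tube is a later and variable time, and these were not modelled.
- *That as many as half of the obtainable deaths are lost.* That confuses the share lost with the gain over the 12-month count, which is 79/378 = 21% to 100/186 = 54% for medians of 6 to 18 months. A share of half is impossible under a constant hazard; it appeared only with a rising hazard and a median near 24 months (53% at Weibull shape 1.5).
- *That every patient is censored at exactly 12 months.* The last form follows the nearest routine visit, its date-of-death field has no cut-off, and no censoring rule is stated. The documents show only that no later collection is described.
- *That everyone could be traced to month 33 at no cost.* Section 12 withdraws patients who lose the ability to consent and keeps only data gathered before that point. Section 8.2 limits access to relevant notes. The fix has to respect both.

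**Conclusion.** The point holds as a limited one. The observation window serves a named secondary outcome poorly, because survival is collected only to the visit nearest 12 months while the study runs on to month 33. Two consequences follow, and they are largest in different situations. With a true median near or above 12 months, the median from tube placement is at risk: about an even chance of being reached at 12 months and almost none from 15. With shorter medians it is reached, and the cost is precision alone. The share of obtainable deaths left uncollected is about 17% at a median of 6 months, rising to 35% at 18. All these figures rest on assumed medians, exponential survival, even accrual and equal groups.

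**What to change.** Keep the 3- and 12-month forms unchanged. Add to Section 7.1 B(iv) one vital-status check at a common close-out date, the end of follow-up at month 33, for all participants not withdrawn. Record alive or dead, with date of death or date last known alive, from centre records. Censor withdrawn patients at withdrawal, including those withdrawn under Section 12 on losing the ability to consent. Use all these data in the Kaplan-Meier and Cox analyses of Section 7.7.

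The cost is one status line per patient and a little site work at close-out, with no extra visit. The sponsor must first confirm that the information sheet and consent wording cover access to records up to that date; if they do not, an amendment would be needed.

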7.7 Data Analysis

Quantitative data analysis

All quantitative data will be managed and analysed using SPSS for Windows version 14.0 (SPSS Inc., 1998). Exploratory data analysis will be initially carried out to establish the distribution of all continuous and categorical variables. Descriptive statistics (means, standard deviations, percentages) will be used to describe the characteristics of the participating centres, the participants and all the main variables of the study. Non-parametric tests (Spearman rank correlation tests and Mann Whitney U tests) will be performed for non-normally distributed continuous variables. Cronbach's alpha (α) coefficients will be determined for the measures that will be used in the study (i.e., MQOL, MCSI, gastrostomy questionnaire) in order to establish their internal consistency.

Continuity corrected Chi-square (χ^2) tests will be performed to determine the difference in the first-month mortality rate and the complication rate following gastrostomy in PEG and PIG/RIG patients. The same tests will be also performed to determine the self-perceived quality of life changes following gastrostomy in PEG and PIG/RIG patients as well as to determine the changes in carer quality of life. Kaplan-Meier survival curves will be used to determine the median survival time from placement of feeding tube, symptom onset and time of diagnosis of the disease in PEG and PIG/RIG patients. Independent samples t-tests will be used to determine the nutritional status changes following gastrostomy in PEG and PIG/RIG patients. Predictors of survival (e.g., respiratory status, site of symptom onset, stage of disease) following gastrostomy will be determined using logistic regression analysis and Cox proportional hazards regressions analysis.

Qualitative data analysis

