Caregiving is a physical strain (For example: lifting in and out of a chair, effort or concentration is required)			
Caregiving is confining (For example: helping restricts free time or I cannot go visiting)			
There have been family adjustments (For example: helping has disrupted my routine; there has been no privacy)			
There have been changes in personal plans (For example: I had to turn down a job; I could not go on holiday)			
There have been other demands on my time (For example: other family members need me)			
There have been emotional adjustments (For example: severe arguments about caregiving)			
Some behaviour is upsetting (For example: incontinence; the person cared for has trouble remembering things; or the person I care for accuses people of taking things)			
It is upsetting to find the person I care for has changed so much from his/her former self (For example: he/she is a different person than he/she used to be)			
There have been work adjustments (For example: I have to take time off for caregiving duties)			
Caregiving is a financial strain			
I feel completely overwhelmed (For example: I worry about the person I care for; I have concerns about how I will manage)			

Gastrostomy Questionnaire

Directions: Here is a list of experiences that other people with gastrostomy have reported. For each of the following items, please circle the number between 1 and 4 which is closest to your experience.

In the last 3 Months how much of a problem was the feeding tube to you:

	Not at All	A Little	Quite a bit	Very much
Pain/discomfort	1	2	3	4
Leakage	1	2	3	4
Dirtying of your clothes from leakage	1	2	3	4
Redness/irritation	1	2	3	4
Blockage	1	2	3	4
Bleeding	1	2	3	4

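### Weight, BMI and complications are recorded at whichever routine visit falls nearest 3 and 12 months, but section 7.7 compares them with tests that ignore the actual follow-up time

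*Protocol*

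**What the plan says.** Protocol section 7.1 sets the timing rule: "At the visits which coincide nearest with 3 months and 1 year post gastrostomy, follow up evaluation forms will be completed". Section 7.2 repeats it for each form; the 12-month form, for example, follows the "usual follow up visit which coincides nearest with 12 months post gastrostomy". No earliest or latest day is given. Section 7.4 states the spacing of those visits: "the participants will continue their standard visits (approximately every 2-3 months) to the neuromuscular clinic".

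Section 7.2 has the 3-month form count complications from the procedure up to that evaluation, and the 12-month form count them from there to the 12-month evaluation. The counting period therefore ends at the actual visit.

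Section 7.7 fixes the tests. For weight and BMI: "Independent samples t-tests will be used to determine the nutritional status changes following gastrostomy in PEG and PIG/RIG patients". For complications, continuity-corrected chi-square "tests will be performed to determine the difference in the first-month mortality rate and the complication rate following gastrostomy". Neither has a term for time since the procedure. Section 7.6 promises to examine disease course, nutritional status and respiratory status, but does not mention elapsed time. It also reports that most participating centres use only PEG or only PIG/RIG.

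**The concern.** In a progressive disease, weight change and cumulative complications both depend on how long the patient has been observed. The stated tests treat a patient weighed at 1.5 months and one weighed at 4.5 months as measured at the same time. Visits follow each centre's usual calendar, and method is largely tied to centre. If PEG centres tended to see patients earlier or later than PIG/RIG centres, the timing difference would appear as a difference between methods, and nothing in section 7.7 would remove it.

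At stake are secondary outcomes i (complications) and iii (weight and BMI) of section 7.5.

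**Working it through.** The protocol gives no figure for visit windows, rate of weight change or SD of change. Its only power calculation concerns first-month mortality and is not an input here. Spacing and targets below come from the protocol; slopes, SDs, group sizes and complication risks are assumptions.

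**1. Range of visit times.** With spacing *s*, the visit nearest target *T* lies within *T* ± *s*/2.
- *s* = 3 months: 3 ± 1.5 = 1.5 to 4.5; 12 ± 1.5 = 10.5 to 13.5 months.
- *s* = 2 months: 2 to 4; 11 to 13 months.

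**2. Does different spacing alone bias the comparison?** If the procedure falls at a random point in the clinic cycle, visit time is uniform on *T* ± *s*/2. Its mean is *T* at any spacing, and its SD is *s*/√12: 2/√12 = 0.58 months and 3/√12 = 0.87 months. Only the scatter differs. At 0.5 kg/month with 3-monthly visits this adds 0.5 × 0.87 = 0.43 kg in quadrature, taking an SD of 5 kg to √(25 + 0.19) = 5.02 kg. A simulation of 2-monthly against 3-monthly centres (200 per group, loss 0.5 kg/month, SD 5 kg, no true difference) gave a rejection rate of 0.052.

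**3. What would bias it.** A gap *g* in mean visit time gives a false difference of slope × *g*. A 1-month gap could arise if visits were counted from the procedure. A 2-monthly clinic then has visits at 2 and 4 months, equally near to 3; if every tie went to month 2, its patients would be seen one month earlier than at a 3-monthly clinic. Evenly split ties give no gap. At 12 months both schedules have a visit at exactly 12, so this route gives no gap there.

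**4. Size if the gap were 1 month.** SE = SD × √(2/150), which is 0.462 kg for SD 4 and 0.577 kg for SD 5. With δ = slope × 1 month, rejection probability = Φ(δ/SE − 1.96) + Φ(−δ/SE − 1.96).

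| Assumed slope (kg/month) | δ/SE, SD 5 | δ/SE, SD 4 | False rejection |
|---|---|---|---|
| 0 | 0 | 0 | 5% |
| 0.25 | 0.43 | 0.54 | 7-8% |
| 0.5 | 0.87 | 1.08 | 14-19% |
| 1.0 | 1.73 | 2.17 | 41-58% |

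With 200 per group and SD 5 kg, the t-test gives 0.08, 0.17 and 0.51 at 0.25, 0.5 and 1.0 kg/month. Over SD 3-8 kg and the same slopes the range is 0.06 to 0.91.

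**5. Complications.** Assume a constant hazard and 40% affected by 3 months: *h* = −ln(0.6)/3 = 0.170 per month, and risk by *t* is 1 − exp(−*ht*). A patient seen at 1.5 months has a 22.5% chance of a recorded complication; one seen at 4.5 months, 53.5%. Averaged over random visit phase, 2-monthly and 3-monthly centres give 39.7% and 39.4%, almost no bias. A systematic 2 v 3 month gap gives 28.9% v 40%, significant about 65% of the time at 200 per group.

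**The case against.** The strongest reply is that a nearest-visit rule is symmetric about its target, so unequal spacing does not shift the mean. Section 7.4 states one spacing for all participants, and its wording ("the participants will continue their standard visits (approximately every 2-3 months) to the neuromuscular clinic as part of routine clinical care") reads as an ongoing calendar rather than one restarted at the procedure. Section 7.6 links centre to method, not visit interval to method. All of this stands. A reader might infer that clinic spacing by itself creates a method difference; step 2 shows that it does not, and the document supplies no gap.

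The assumed slopes can also be challenged. Section 6 describes tube feeding as stabilising body weight, and near-zero slopes leave the error at about 5% whatever the gap. That stands too, so the higher rejection rates are conditional illustrations, not expected error rates.

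It is also said that windows and time adjustment belong in an SAP, that section 7.1 foresees refining the analysis plan after the centre survey, and that routine-visit collection suits a pragmatic study. The collection rule is indeed reasonable, and no dates are lost. But section 7.7 does not leave the analysis open: it names unadjusted tests for data whose follow-up time is known to vary.

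A reader might also fault the Gastro-Qu lead-in, "In the last 3 Months how much of a problem was the feeding tube to you", because completion may not fall at exactly 3 months. Tying recall to tube insertion instead would make its length vary with completion date, so that is not clearly better. At a 2-month completion the current wording does no harm, since there was no earlier tube to report on.

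**Conclusion.** The point holds as a weakness in the stated analysis, not as a demonstrated bias. Recorded follow-up can run from 1.5 to 4.5 and from 10.5 to 13.5 months, and the named tests ignore it. With equal mean visit times the cost is a little extra scatter. With a systematic 1-month gap between methods, false rejection for weight change would be about 14-19% at 0.5 kg/month (150 per group, SD 4-5 kg), higher at steeper slopes and about 5% if weight is stable. The gap, slopes and SDs are assumptions; the protocol neither shows nor excludes such a gap.

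The reach is limited to secondary outcomes. First-month mortality and the survival analyses rest on dates of death and are unaffected. MQOL and MCSI are exposed only loosely: section 7.2 schedules them at baseline and 3 months only, and section 8.2 lets them be posted. The change should be made because it is nearly free, not because the main conclusion is in danger.

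**What to change.** Amend section 7.7 as follows.

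- **Weight and BMI:** replace the plain t-tests with an analysis on actual dates, for example a mixed model on the baseline, 3- and 12-month values with time in days relative to the procedure. Keep baseline weight at its own recorded date, so that the wait from referral to procedure is counted.
- **Complications:** account for exposure up to the evaluation date. The forms record ticks rather than onset dates, so a binary model with a complementary log-log link and log exposure time as offset would serve. For patients who die first, exposure ends at the date of death.
- **Reporting:** give the distribution of visit day by method, so that readers can see whether a gap existed.

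Keep all values rather than excluding those outside a window, and leave the Gastro-Qu wording unchanged. The evaluation forms already carry the procedure, evaluation and death dates, so no new data collection is needed. The cost is slightly more analysis work.
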